## **13. Withdrawal of Subjects**

During tDCS application, subjects will describe physical sensations such as tingling or itching using a 10-point anchored Likert scale. Administration of tDCS will be stopped immediately if subjects report a 7 or above for discomfort, or if subjects wish to stop at any time. Subjects will also have their mood, energy, pain, and arousal levels assessed using visual analog 10-point scales. These checks will occur every ten minutes during the stimulation session. Any report of pain or decreased level of arousal by the patient will result in stopping of stimulation.

If at any time a participant wishes to withdraw from the study, they will be debriefed by the study coordinator or principal investigator as to the reason for their withdrawal. They will be offered the chance to partially withdraw from the stimulation protocol and continue in the data collection aspect if they so wish. Otherwise the participant will then be thanked for their time, and they will be compensated for the extent of their participation.

If the participant wishes to withdraw, they will be asked if they will allow data already collected on them to be used in the study analysis. If not, the data associated to their identifying code will be purged from the study database.

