Statistical analyses will utilize the CTSC Biostatistics core. Power analyses and statistical analysis strategy were determined with our statistician [name], who will continue to provide recommendations and support throughout the project. Sufficient group sizes were determined on the basis of data derived from preliminary studies. Clark and colleagues found an effect size of Cohen's  $d = 1.2$  for tDCS to induce improvements in cognition. For our power calculations we will assume a more conservative effect size of  $d = 0.7$  which is consistent with a recent meta-analysis of tDCS effect sizes. With 40 tDCS treatment patients compared to 40 sham patients and an effect size of 0.7, we have 80% power to detect effects of active versus sham treatment in a two-sample t-test. Power in the linear mixed model analysis should be superior that that of the t-test. For Aim 1.1, the central analyses evaluate group (active vs. sham) differences in the EEG data and on the three Examiner composite variables across the three initial time points (before, immediately after, and 1 month after tDCS stimulation protocol). To test this hypothesis, three separate linear mixed models analyses will be performed using the three Examiner composite scores (Fluency, Cognitive Control, Working Memory) as dependent variables. In each analysis, we will incorporate three covariates that may predict variation in learning (severity: mild vs. moderate, premorbid intelligence: WTAR score, and symptom burden: NSI). This will allow us to determine predictors of treatment response (Specific Aim 1.3). Sex, ethnicity, and age will also be entered into the statistical model. The effects of these covariates will be estimated by constructing appropriate contrasts in model effects. A similar set of analyses will evaluate group differences on the variables assessed in our long-term oral/phone follow-up (five data points: (1) before tDCS, (2) immediately after tDCS, (3) 1 month post-tDCS, (4) 6 months, and (5) 1 year) for Aim 1.2. For these analyses dependent variables will be the total cognitive items score of the NSI and the PROMIS-29 profile total score). Significant effects will be followed up with more fine-grained analysis of the components of composite scores. The use of linear mixed-models minimizes the adverse impact of a missing data point, which may well occur in a longitudinal clinical study such as this. Expected attrition will be taken into account with an intention-to-treat analysis. Missing data patterns will be analyzed to assess the extent to which they are informative (in contrast to missing at random), and analyses adjusted accordingly. All EEG data will undergo standard preprocessing (e.g. motion correction, spatial normalization) and quality control prior to statistical modeling. Depending on the specific question of the study, data may be analyzed using the general linear model, independent components analysis, machine learning techniques, or a variety of other standard approaches for neuroimaging data.

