
## 12. Provisions to Monitor the Data to Ensure the Safety of Subjects

Data safety and monitoring will be carried out to ensure and maintain the scientific integrity of this project and to protect the safety of our participants. Safety monitoring is the process during the study that involves review of accumulated outcome data for groups of subjects to determine if any of the procedures practiced should be altered or stopped. Ultimately, the PI ([name]) will be responsible for monitoring the safety of the study and complying with the reporting requirements. An independent Data Safety and Monitoring Board (DSMB) will review the study data on a quarterly basis with the PI to ensure participant safety. The DSMB for this study will be composed of [name], the medical director of the Electroconvulsive Therapy Service at UNM, and [name], staff epileptologist of the Epilepsy Monitoring Unit at UNM. Their experience in assuring safety of brain stimulation therapies and seizure monitoring protocols make them ideally suited to serving on this project's DSMB. Continuous, close monitoring of participant safety will include prompt and frequent reporting of safety data (i.e., adverse/serious adverse events) to the

**PROTOCOL TITLE:** Transcranial direct current stimulation for treatment of deficits after traumatic brain injury.

DMSB, the University of New Mexico Health Sciences Center Institutional Review Board (UNMHSC IRB) and/or appropriate NIH staff with oversight responsibility. The PI will provide a summary of the safe conduct of the study to NIH on an annual basis as part of the progress report. All AEs occurring during the course of the study will be collected, documented, and reported to the UNMHSC IRB.

The review of data may result in early termination of the study, amendment to the protocol, or changes to the data collection plan or study forms if it appears that there are adverse events occurring at a rate significantly greater than that found in similar tDCS studies involving subjects with neurological disorders (ie. stroke). Should the protocol or data collection plans or study forms be amended as a result of data review, the IRB will be notified and the amendment approved prior to study amendment implementation. In addition, the participants will be notified of any significant new findings that develop during the course of research that may affect their wish to continue participation in the study.

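### The purge of data from withdrawn participants makes no exception for allocation, exposure or adverse events, which contradicts the intention-to-treat and adverse-event commitments

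*Combined protocol and SAP*

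**What the plan says.** Section numbers here are those in the body of the document, which differ from its table of contents.

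Section 13 sets out three steps for a participant who wants to leave. First, stimulation can stop while assessments go on: "They will be offered the chance to partially withdraw from the stimulation protocol and continue in the data collection aspect if they so wish". Second, a participant who withdraws is asked about data already held: "they will be asked if they will allow data already collected on them to be used in the study analysis". Third, if the participant refuses, "the data associated to their identifying code will be purged from the study database". No class of record is exempt.

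Section 11 (Data Analysis), repeated in Section 14 (Data Management/Confidentiality), says "Expected attrition will be taken into account with an intention-to-treat analysis" and "Missing data patterns will be analyzed to assess the extent to which they are informative".

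Section 12 (safety monitoring) says "All AEs occurring during the course of the study will be collected, documented, and reported to the UNMHSC IRB". It also provides for quarterly DSMB review of study data, and for possible termination or amendment if adverse events occur at a significantly higher rate than in similar tDCS studies.

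Sections 10 and 18 place randomization at the time of consent.

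**The concern.** Because allocation happens at consent, a person who is later purged has an assigned arm and may have been stimulated. After the purge the study database no longer shows that this person was randomized, how many sessions were given, why the person left, or what events occurred. Two things follow.

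- The analysed set is no longer the randomized set, although the plan calls the analysis intention-to-treat.
- Adverse-event rates in the database can lose both the event and the person from the denominator, while Section 12 relies on a rate to judge safety.

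The loss is also not protected from allocation. Active current is 2.0 mA and sham is up to 0.2 mA (Section 10). The debriefing at withdrawal may be done by the study coordinator, who is unblinded. The plan does not say who asks the data-use question. None of this implies misconduct, but nothing in the rule guards against loss that differs by arm, and no count of purges is required from which such loss could be seen.

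**Working it through.** The purge rule carries no figure of its own, so the main check sets the texts side by side. The arithmetic then shows how large the effect could be.

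**1. Can the statements hold together?**
- *Intention-to-treat.* It needs every randomized participant to be accounted for in the assigned arm. A purged participant has no record of allocation in the study database, so this fails for any purge count above zero.
- *Missing-data patterns.* A pattern can be studied only for someone whose row exists. Purged participants have none.
- *Mixed model.* Section 11 offers it as protection against a missing data point. It uses the visits that are present and cannot represent a person with no visits at all.
- *Adverse events.* Section 12 wants all events documented. Section 13 deletes them from the database with the rest.

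**2. How many people?** Section 31 gives 2 withdrawals for intolerable sensation in 138 subjects, and separately an intolerance rate of about 1%. Section 10 gives 40 active TBI patients and 40 active controls. Expected number = n × p; P(at least one) = 1 − (1 − p)^n.
- p = 2/138 = 1.45%; exact 95% interval 0.2% to 5.1%.
- 40 active TBI patients: 40 × 0.01 = 0.4 to 40 × 0.0145 = 0.58 expected; P(at least one) = 33% to 44%.
- 80 active participants: 0.8 to 1.16 expected; P(at least one) = 55% to 69%.
- At the upper limit: 40 × 0.0514 = 2.1, or 80 × 0.0514 = 4.1.

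For intolerance these rates give a ceiling on purges, since refusal of data use is also required. Withdrawal for other reasons is not quantified in the document. The number of sessions the 138 subjects received is not stated, while this trial gives up to ten.

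**3. Safety counts (illustration; the event counts are assumed).**
- Two active TBI patients leave with a skin reaction and both are purged: 2/40 = 5.0% becomes 0/38 = 0%.
- Four have events and two of them are purged: 4/40 = 10% becomes 2/38 = 5.3%.

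**4. Power.** The plan states 80% for 40 versus 40 at d = 0.7 with a two-sample t-test, without giving alpha. At two-sided 0.05 (assumed) the t-test gives 87.1%, so the plan's figure is conservative on that reading. Purging 2 active patients gives 86.2%, and purging 4 gives 85.3%.

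**5. Efficacy bias for people who had a post-treatment score.** If k of 40 active patients are purged and score g SD worse than those retained, the arm mean rises by (k/40) × g. For k = 2 and g = 0.5 to 1.0 (assumed), this is 0.025 to 0.05 SD, with type I error of about 5.1% to 5.6% instead of 5%.

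**The case against.** The strongest reply is that the rule will seldom apply and that much survives it. A purge needs full withdrawal and also refusal of data use, after partial withdrawal has been offered. Section 12 requires reporting outside the database: "Continuous, close monitoring of participant safety will include prompt and frequent reporting of safety data" to the DSMB, the IRB and/or NIH staff. The debriefing covers the reason for leaving, and the device keeps its own log of the stimulation protocol. The purge also honours a participant's refusal, which is an ethical choice. The consent form was not available for this check, so what participants are told about retention is unknown.

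This limits the size of the problem. It does not reconcile the texts, because none of those other records is linked to the arm-level tables or exempted in Section 13.

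A reader might infer three stronger things that the documents do not support.

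- **Efficacy is inflated by a material amount.** If 1 to 6 of 40 active patients with no benefit were purged and the rest had d = 0.7, the effect in all randomized patients would be 0.7 × (40 − k)/40 = 0.68 to 0.60, an apparent overstatement of 3% to 18%. That comparison assumes a post-treatment outcome for every purged person. Someone who leaves during the sessions has only a baseline score. If baseline is unrelated to leaving, keeping that score would hardly change the estimated treatment effect. That bias would come from dropout itself, and keeping the record would not remove it. Six of 40 is also far above what 2/138 suggests.
- **The loss falls mainly on the active arm.** Sections 3 and 10 describe sham sensation as similar or somewhat similar, Section 31 claims effective blinding, and no withdrawal rate is given by arm.
- **Adverse events disappear altogether.** Those already reported to the IRB or DSMB remain there.

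**Conclusion.** The contradiction stands whatever the purge rate. Applied as written, Section 13 produces a set that is not intention-to-treat and can leave safety counts incomplete in the study database, in the arm-level safety tables, and possibly in what the DSMB reviews each quarter. That last point is uncertain, because the plan does not say which extract the DSMB sees.

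The expected size is small: fewer than one intolerance withdrawal among 40 active TBI patients at the group's own rates, and about two at the upper 95% limit, before allowing for refusal. The effect on power and on the primary comparison is slight. Safety is where small numbers matter, since two purged events can turn 5% into zero. Loss could differ by arm, but the direction is not established, and no percentage for overstated efficacy should be attached to this point. These sizes rest on the 2/138 experience carrying over to this trial and on the assumed event counts. The change is worth making because the plan requires no record from which the loss could later be measured.

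**What to change.** Amend Section 13, and align the consent wording, as follows.

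- Always keep, in coded form, the allocation, sessions received, reason for withdrawal and all adverse events, and count them in the assigned arm.
- Where the IRB allows, also keep outcome data collected before withdrawal and analyse them as randomized.
- Where the IRB requires outcome data to be deleted on request, report the number purged by arm and describe the efficacy set as excluding them, not as full intention-to-treat.
- Retain the existing offer to stop stimulation and remain in follow-up.
- Add a cross-reference in Sections 11, 12 and 14 so that the analysis and safety text match.

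The cost is one IRB amendment to the protocol and consent form. No clinical rule changes. The real downside is that participants can no longer have these minimal coded records deleted, and they must be told so at consent.

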## **14. Data Management/Confidentiality**

Neuropsychological testing and questions regarding depression, post-concussive symptoms, and quality of life will be collected from all participants. All forms of data described above will be recorded on to paper and pencil or computerized data forms that do not contain identifying information. A separate file contains contact information for the purpose of mailing the radiology review letter and future contact, in needed, but has no personal data or protected health information that is collected as part of the study.

No personally identifying information will be coded on the questionnaires, neuropsychological measures, brain imaging data, or any other data recording instruments, assuring confidentiality to the best of our ability. Subject identification numbers are assigned to each participant. Only the PI and HIPAA-trained project coordinator have access to the file that links names with subject numbers. All data are stored in locked file cabinets in a locked office, on password-protected computers located behind a secure and maintained firewall. Data will also be collected and stored on a drive only accessible by the research team on a secure MRN server, and/or in the COINS database on an Amazon Web Services (AWS) HIPAA compliant cloud server. The cloud based server and any other electronic

PROTOCOL TITLE: Transcranial direct current stimulation for treatment of deficits after traumatic brain injury.

storage is accessible only by the research team, and data is coded with the unique subject identification numbers.

All data are collected by the PI, or trained research assistants who have completed on-line training in human subjects' research, HIPAA and research integrity; who are trained in our lab on research data management and confidentiality; and who are trained to criterion on project protocol. Data will be collected specifically for this proposed research project.

Participants will be assured that all records will be kept confidential in research files located in a locked office and entered into a password-protected computer located behind a secure and maintained firewall. Breach of confidentiality is highly unlikely because all personally identifying information will be kept separate from data collected, and will be linked only by a master subject identification list maintained by the project coordinator and PI. MRN retains the link between identifiers and URSI indefinitely for the potential future benefit to the research participant. Specifically, it may become medically advantageous in the future for a former participant to have access to the clinical information that is present in most radiological scans. For example, if a participant is diagnosed with a neurological condition (e.g. multiple sclerosis, glioblastoma, TBI, etc.) it may be clinically beneficial for the participant's physician to have access to a research scan that was performed at an earlier time-point to determine disease course and severity. In order to address any concerns regarding coercion, participants will be informed that they are free to choose not to participate and may withdraw at any time (this is included in the consent form).

Finally, because any information gathered as part of this study is confidential, we cannot intervene on an individual level unless it is discovered that there is imminent threat to the life of the participant, to others, or if there is any indication of child or elder abuse. In these rare cases, we would consider the risk to self and others and intervene as we would if the individual endorsed other intent to harm themselves (i.e., talk with the participant and express concern, present the participant with local options for treatment, encourage him/her to disclose the issue to authorities, and if unwilling, inform them that we must disclose the information to authorities for their (or others') safety.

We will also provide all participants and their families with a referral list of community support, treatment, and educational resources about TBI. This information will also be explained during the consent process. In addition, if a participant's status with respect to any of the study criteria change during the experiment (i.e., initiation of substance abuse), the participant's participation in the study may be terminated without their consent. Our consent form will include a statement regarding anticipated circumstances under which the subject's participation may be terminated by the investigator without regard to the subject's consent and a statement indicating that significant new findings developed during the course of the research which may relate to the subject's willingness to continue participation will be provided.

Statistical analyses will utilize the CTSC Biostatistics core. Power analyses and statistical analysis strategy were determined with our statistician [name], who will continue to provide recommendations and support throughout the project. For Aim 1.1, the central analyses evaluate group (active vs. sham) differences on the three Examiner composite variables across the three initial time points (before, immediately after, and 1 month after tDCS stimulation protocol). To test this hypothesis, three separate linear mixed models analyses will be performed using the three Examiner composite scores (Fluency, Cognitive Control, Working Memory) as dependent variables. In each analysis, we will incorporate three covariates that may predict variation in learning (severity: mild vs. moderate, premorbid intelligence: WTAR score, and symptom burden: NSI). This will allow us to determine predictors of treatment response (Specific Aim 1.3). Sex, ethnicity, and age will also be entered into the statistical model. The effects of these covariates will be estimated by constructing appropriate contrasts in model effects. A similar set of analyses will evaluate group differences on the variables assessed in our long-term oral/phone follow-up (five data points: (1) before tDCS, (2)

**PROTOCOL TITLE:** Transcranial direct current stimulation for treatment of deficits after traumatic brain injury.

immediately after tDCS, (3) 1 month post-tDCS, (4) 6 months, and (5) 1 year) for Aim 1.2. For these analyses dependent variables will be the total cognitive items score of the NSI and the PROMIS-29 profile total score). Significant effects will be followed up with more fine-grained analysis of the components of composite scores. The use of linear mixed-models minimizes the adverse impact of a missing data point, which may well occur in a longitudinal clinical study such as this. Expected attrition will be taken into account with an intention-to-treat analysis. Missing data patterns will be analyzed to assess the extent to which they are informative (in contrast to missing at random), and analyses adjusted accordingly. Data will be stored in Excel spreadsheet form as well as on hard copies.

Digital data will be stored on secure encrypted drives located behind a secure firewall. Data will be reviewed by the PI for quality control.

Human subjects in the proposed protocol may receive screening and diagnostic interviews, phenotypic assessment (including emotional, cognitive and behavioral functioning), including interview and questionnaire queries regarding their mental health history, substance use history, and history of prior brain injuries and other neurological disease or injury. A link between identifiers and data will be created; It will be stored separately in a locked file cabinet behind locked doors in a secure area of the Clinical Core for the duration of the study (5 years). It will be disposed of and shredded after the conclusion of the final data analysis. Only the PI and trained research personnel will have access to the data, and will be solely responsible for receipt or transmission of the data. No data will be collected, transmitted, and/or stored via the internet. No data will be collected via audio/digital recordings. No data will be collected on video recordings or via photographs. Data will be stored for the duration of the study and will be destroyed after the final data analysis is complete. It will be stored at the Clinical Core on secured encrypted drives (digital) and in locked file cabinets behind locked doors in a secure area of the Clinical Core.

A Certificate of Confidentiality (CoC) has been received from the NIH once IRB approval is in place. The CoC helps the researchers to protect the privacy of the subjects enrolled in the study from compulsory legal demands, such as court orders and subpoenas, for identifying information or identifying characteristics of a subject. This study is eligible for a CoC because it will collect personally identifiable, sensitive information about subjects, and will be federally funded. Sensitive information in this study includes information about a subject's neuropsychological performance and emotional states. This is information that if released could be damaging to a subject's financial standing, employability, or reputation within the community; pertains to a subject's psychological well-being or mental health; and might lead to social stigmatization or discrimination if it were disclosed.

